2 STUDY OBJECTIVES AND ENDPOINTS

Recent clinical trials have demonstrated median PFS as high as 5 months with the combination of low dose ipilimumab (1 mg/kg IV every 3 weeks) in combination with anti-PD-1 therapies in patients with anti-PD1 refractory cutaneous melanoma. As such, we will use the 5 month mPFS as the benchmark for the design of this clinical trial. In order to show a 4 month improvement in mPFS (with a power of 0.8 and a one-sided test given a type I error rate of 0.05), a total of 41 subjects would need to be enrolled. This signal seeking pilot study will initially enroll 25 subjects at our site (single institution) in less than 2 years. If this treatment combination results in a *mPFS of at least 8 months or an ORR of 45% or higher*, we will review these results with BMS and Exelixis and propose protocol and budget amendments to add 1-2 additional sites to expedite enrollment to a total of at least 41 subjects.

Primary Objective

The primary objective of this clinical trial is to evaluate the clinical efficacy and progression free survival of the triplet combination of ipilimumab + nivolumab + cabozantinib in patients with anti-PD-1/PD-L1 refractory metastatic cutaneous melanoma.

Secondary Objectives:

- Safety/Tolerability (CTCAE v5.0)
- Objective response rate (iRECIST)
- Overall survival
- Correlative translational studies (paired pre-treatment and day #15 on-treatment tumor biopsies for characterization of tumor infiltrating immune cell profiling and gene expression changes)

Primary endpoint:

Progression free survival will be defined as the time between the date of enrollment and the first date of documented progression (per iRECIST), as determined by the investigator, or death due to any cause, whichever occurs first. Cumulative incidence functions will be displayed and summarized for the median time to progression as well as percentage of patients without disease progression at 12, 18, and 24 months.

Secondary endpoints:

- 1. Objective response rate (iRECIST)
- 2. Duration of response
- 3. 6, 12 and 24 month progression free survival
- 4. 12 month overall survival
- 5. Incidence of grade ≥3 treatment related adverse events (CTCAE v5.0)
- 6. Correlative molecular profiling

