8 STATISTICAL CONSIDERATIONS

Data and Statistical plan:

Recent clinical trials have demonstrated median PFS as high as 5 months with the combination of low dose ipilimumab (1 mg/kg IV every 3 weeks) with anti-PD-1 therapies in patients with anti-PD1 refractory cutaneous melanoma. In this clinical trial, we will use the 5 month mPFS as our benchmark. In order to show a 4 month improvement in mPFS over the 5 month historical data benchmark (with a power of 0.8 and a one-sided test given a type I error rate of 0.05), a total of 41 subjects would need to be enrolled.

This signal seeking pilot study will enroll 25 subjects at our site (single institution) in less than 2 years. If we find that this treatment combination results in a *mPFS of at least 8 months or an ORR of 45% or higher*, we will review these results with BMS and Exelixis and propose protocol and budget amendments to add 1-2 additional sites to expedite to a total of at least 41 subjects to be enrolled in a rapid timeframe.

Descriptive Statistics:

Descriptive statistics will be provided for all baseline, efficacy, and safety variables, as appropriate. Frequency counts and percentages will be provided for categorical data. Mean (standard deviation), median (interquartile range) will be calculated for continuous variables.

Statistical Analyses for Primary and Secondary Endpoints:

Primary endpoint: The progression-free survival (PFS) analyses will be performed considering the risk of dying from any cause before experiencing progression related events using the competing risk regression method²⁴. Cumulative incidence functions will be displayed and summarized for the median time to progression as well as percentage of patients without disease progression at 12, 18, and 24 months.

Secondary endpoints: ORR will be determined as the rate of the confirmed best overall response of either PR or CR per iRECIST. Using the efficacy evaluable analysis set, the Kaplan-Meier method will be used to estimate PFS, OS and DOR, and the summary statistics (e.g., 12-month survival and median CONFIDENTIAL - Cabozantinib + Nivolimab + Ipililumab Protocol Required Elements

Page 66 of 92

survival with 95% confidence intervals). DOR will be estimated only among responders (i.e. participants achieving at least once CR or PR). Data visualization tools such as waterfall plots (% change in tumor size) or swimmer plot (DOR) will be used to display the data.

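### The primary endpoint is PFS with death as an event, but the primary analysis makes death a competing risk and reports time to progression, which can only match or overstate PFS

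*Combined protocol and SAP*

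**What the plan says.** Section 2, Primary Objective: "The primary objective of this clinical trial is to evaluate the clinical efficacy and progression free survival of the triplet combination". The primary endpoint in the same section runs from enrollment to documented progression by iRECIST "or death due to any cause, whichever occurs first". Death is therefore part of the endpoint event.

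The next sentence of that endpoint paragraph, repeated in Section 8, gives the summary: "Cumulative incidence functions will be displayed and summarized for the median time to progression as well as percentage of patients without disease progression". The landmarks are months 12, 18 and 24. Section 8 alone names the method. The PFS analyses will be done "considering the risk of dying from any cause before experiencing progression related events using the competing risk regression method".

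A second PFS estimate appears under Secondary endpoints in Section 8: "Using the efficacy evaluable analysis set, the Kaplan-Meier method will be used to estimate PFS, OS and DOR". Section 2 lists "6, 12 and 24 month progression free survival" as a secondary endpoint. The efficacy evaluable set is not defined in the document.

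The decision figures are worded as median PFS: "In this clinical trial, we will use the 5 month mPFS as our benchmark", and expansion beyond 25 patients is considered if there is an "mPFS of at least 8 months or an ORR of 45% or higher".

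**The concern.** Death cannot be both a component of the event and a competitor to it. If death counts towards PFS, no competing risk is left. If death competes, the quantity estimated is time to progression, and the primary result does not estimate the defined primary endpoint.

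The discrepancy runs one way. A patient who dies without documented progression counts as a failure in PFS, but stays in the percentage without progression for good. For the same PFS curve, the more of its events that are deaths, the better the primary summary looks.

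Two uses of the result are exposed. The first is the reported primary result, in which percentages at 12 and 24 months would stand beside secondary PFS figures that may differ from them. The second is the comparison with the 5-month benchmark and the 8-month trigger, if the cumulative incidence median is the one used. The plan does not say.

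**Working it through.** **Inputs from the document.** Benchmark median PFS 5 months, trigger 8 months, 25 patients (Section 8); restaging every 12 weeks, plus or minus 1 week (Section 4.2 table).

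**Assumptions not in the document.** Exponential event times with true median PFS 5 months, so λ = ln 2/5 = 0.1386 per month. The share q of first events that are deaths is shown at 5, 10, 20 and 25%; nothing in the document favours the upper values.

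The plan gives no figure of its own on this point. Its 41 subjects rest on median PFS of 9 against 5 months and do not enter here.

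**1. Identity (no assumption about q).** With CIF the cumulative incidence function, 1 − CIF of progression(t) = PFS(t) + CIF of death without progression(t). With 25 patients fully followed to a landmark, each such death before it adds 1/25 = 4 percentage points. With none, the two figures agree.

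**2. Median.** CIF(t) = (1 − q)(1 − e^(−λt)). Setting this to 0.5 gives t = −ln(1 − 0.5/(1 − q))/λ. For q = 10%: −ln(1 − 0.5556)/0.1386 = 5.85 months.

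**3. Twelve months.** PFS = e^(−12λ) = 18.9%. Percentage without progression = 1 − (1 − q)(1 − 0.189). Chance that at least one of 25 patients has such a death before month 12 = 1 − (1 − q × 0.811)^25.

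**4. Chance that 25 patients give a median of at least 8 months, continuous observation.** This needs at most 12 events by month 8. The event probability is 1 − e^(−8λ) = 0.670 for PFS and (1 − q) × 0.670 for progression; the chance is the binomial probability of 12 or fewer out of 25.

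**5. The same on a rigid 12-week grid.** Scans fall every 84/30.4375 = 2.76 months. Progression is recorded at the next scan if the patient is alive. Event probabilities by month 8 are 0.543, 0.550, 0.566 and 0.573 for PFS, and 0.503, 0.472, 0.411 and 0.381 for progression.

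| | q = 5% | 10% | 20% | 25% |
|---|---|---|---|---|
| CIF median, months (PFS: 5.0) | 5.4 | 5.9 | 7.1 | 7.9 |
| Without progression at 12 months (PFS: 18.9%) | 23% | 27% | 35% | 39% |
| At least one such death before month 12 | 64% | 88% | 99% | over 99% |
| Median ≥ 8, continuous: Kaplan-Meier | 3.8% | 3.8% | 3.8% | 3.8% |
| Median ≥ 8, continuous: CIF | 8% | 15% | 36% | 49% |
| Median ≥ 8, grid: Kaplan-Meier | 33% | 30% | 25% | 23% |
| Median ≥ 8, grid: CIF | 49% | 61% | 82% | 89% |
| Two medians identical, continuous | 51% | 25% | 6% | 2% |
| Two medians identical, grid | 78% | 56% | 24% | 14% |

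The last two rows come from 40,000 simulated trials, which also agree with the grid trigger rows. Letting each scan vary within 1 week changes no trigger figure by more than about 1 point. The CIF median was never below the PFS median in the continuous simulation.

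**6. Two cautions on the grid rows.** The 12-week interval by itself lifts the Kaplan-Meier figure from 3.8% to between 23 and 33%; that is a separate matter. Extra scans when clinically indicated, which Section 4.2 allows, would move results towards the continuous rows.

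**The case against.** The strongest reply is that Kaplan-Meier PFS, with a median and 95% confidence interval, is already planned. The benchmark and trigger are worded as median PFS, while the competing-risk summary carries a different name. A sensible reader would take the trigger to mean the Kaplan-Meier median. If the cumulative incidence of death is also displayed, PFS can be recovered. This is a fair reading, but the text never states it, and it leaves the stated primary analysis estimating something other than the primary endpoint.

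The effect is also weakest on the median, which is what the trigger uses. That stands: with few such deaths the two medians often coincide, as the table shows.

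The grid levels depend on taking 5 months as the continuous-time median, although a reported benchmark probably already contains some scan delay. That also stands. With an assumed true median of 3.6 months (5 months less about half a scan interval), the grid chances fall to 5, 4, 3 and 2% by Kaplan-Meier against about 12, 23, 52 and 67% by cumulative incidence. The levels move; the gap remains.

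Finally, this is a signal-seeking pilot: the trigger leads only to a review with the two supporting companies and a proposed amendment, and the response-rate criterion can meet it alone. This limits the harm but does not make the primary result PFS.

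**Conclusion.** The concern holds, and it must be fixed. As written, the primary analysis does not estimate the defined primary endpoint, and any discrepancy is upward. The direction, and the 4 points per death at a landmark with 25 fully followed patients, need no assumed death rate. The sizes for the median and the trigger rest on exponential times, a true median of 5 months and an assumed q; they range from slight at 5% to a cumulative incidence median of 7.9 months at 25%. If no patient dies without documented progression, the two estimates agree in the same patients. Whether the error reaches the benchmark or the trigger is uncertain, because the plan does not name the estimate.

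**What to change.** 1. Section 8, Primary endpoint: replace both sentences with: *PFS (first of iRECIST progression or death from any cause) will be estimated by the Kaplan-Meier method in all patients who received at least one dose of study therapy. The median with 95% CI and PFS rates at 6, 12, 18 and 24 months will be reported. This is the only PFS estimate used for the 5-month benchmark and the 8-month criterion.*
2. Section 2, Primary endpoint: replace the cumulative incidence sentence with: *Median PFS and PFS rates at 6, 12, 18 and 24 months will be reported as described in Section 8.*
3. Section 8, Secondary endpoints: remove PFS from the Kaplan-Meier list, leaving OS and DOR.
4. Section 2, secondary endpoint 3: add *read from the primary Kaplan-Meier PFS curve*.

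The cumulative incidence of progression with death competing may stay as a supportive display labelled time to progression. The treated population fits Section 4.5, which replaces patients whose enrollment is canceled before therapy, and the at-least-one-dose rule used for safety in Section 8.

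The cost is wording in four places and a routine amendment with the approvals in Section 11; no new data or patients are needed. The reported figure will be less favourable if deaths precede documented progression. The analysis set for OS and DOR, the censoring rule, the test against the benchmark and the scan interval are separate matters that this change does not settle.

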7 SAFETY

7.1 Adverse Events and Laboratory Abnormalities

7.1.1 Adverse Events (AEs)

An AE is any untoward medical occurrence in a patient or clinical trial subject who has been enrolled in a clinical study and who may have been administered an investigational product, regardless of whether or not the event is assessed as related to the study treatment. An adverse event can therefore be any unfavorable and unintended sign (including an abnormal laboratory finding), symptom, or disease temporarily associated with the use of an investigational product, regardless of whether or not the event is assessed as related to the investigational product. This requirement includes specific events or symptoms associated with cancer progression or general clinical deterioration to ensure potential toxicities are not overlooked. Radiographic progression without associated clinical sequalae is not considered an AE: terms such as 'disease progression' should be avoided. An adverse event can arise from any use of the drug (eg off-label use, use in combination with another drug) and with any route of administration, formulation, or dose, including an overdose. This definition also includes AEs associated with medication errors and uses of the investigational product outside what is in the protocol, including misuse and abuse. Pre-existing medical conditions that worsen during the study should be recorded as AEs. Abnormal laboratory values, ECG findings, or vital signs are to be recorded as AEs if they meet the criteria described in this protocol.

All untoward events that occur after start of study therapy through 30 days (100 days for SAEs and certain other events [See AEs of Special Interest Table]) after the last study treatment are to be recorded by the investigational site.

At each scheduled and unscheduled visit, AEs are to be identified and assessed based upon study procedures, routine and symptom-directed clinical investigations, and subject query/report.

Seriousness, severity grade, and relationship to study treatment will be assessed by the Investigator.

Severity grade will be defined by the current version of the National Cancer Institute (NCI)-Common Terminology Criteria for Adverse Events (CTCAE). This study will use the NCI CTCAE v5.0.

Assessment of the relationship of the AEs to individual study treatment by the Investigator is based on the following two definitions:

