- Not Related: An event is assessed as not related to study drug if it is attributable to another
 cause and/or there is no evidence to support a causal relationship to the study treatment.
- Related: A related AE is defined as an AE where a causal relationship between the event and the study treatment is a reasonable possibility. A reasonable causal relationship is meant to convey that there are facts (e.g., evidence such as dechallenge/rechallenge) or other clinical arguments to suggest a causal relationship between the AE and study treatment. Possibly and probably related AEs should be documented as related.

Non-serious Adverse Events (AE) are to be provided to BMS in aggregate via interim or final study reports as specified in the ISR agreement or, if a regulatory requirement [eg, IND US trial] as part of an annual reporting requirement.

Non-serious AEs should be followed to resolution or stabilization, or reported as SAEs if they become serious. Follow-up is also required for non-serious AEs that cause interruption or discontinuation of study drug and for those present at the end of study treatment as appropriate.

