Using the safety evaluable analysis set, the incidence of having Grade ≥ 3 AEs will be determined for study participants that received at least one dose of their assigned treatment. The point estimate and 95% confidence interval will be reported.

For correlative molecular profiling endpoint, paired t-test or Wilcoxon signed-rank test will be performed to evaluate tumor infiltrating immune cell profiling and gene expression changes between pre- and post-treatment.

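### Section 8 estimates Grade ≥3 adverse events of any cause although secondary endpoint 5 is treatment-related events, and its duration-of-response set, read literally, is not limited to confirmed responders

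*Combined protocol and SAP*

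**What the plan says.** **Safety.** Section 2 lists secondary endpoint 5 as "Incidence of grade ≥3 treatment related adverse events (CTCAE v5.0"). The corresponding secondary objective is broader, "Safety/Tolerability (CTCAE v5.0"), with no mention of relatedness. Section 8 plans the analysis in the safety-evaluable set: "the incidence of having Grade ≥ 3 AEs will be determined for study participants that received at least one dose of their assigned treatment". It adds: "The point estimate and 95% confidence interval will be reported". No relatedness qualifier appears there.

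Section 7.1.1 defines an adverse event "regardless of whether or not the event is assessed as related to the study treatment". The same section provides the data needed to separate related from unrelated events: "Seriousness, severity grade, and relationship to study treatment will be assessed by the Investigator", on a two-level scale with the instruction "Possibly and probably related AEs should be documented as related".

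The general descriptive paragraph of Section 8 covers safety variables where appropriate and says "Frequency counts and percentages will be provided for categorical data". It names no treatment-related rate and no interval.

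**Response.** In Section 8, under the secondary endpoints, the objective response rate is based on a confirmed best overall response of PR or CR per iRECIST. Duration of response is limited to responders, who are then defined in parentheses as anyone who reached CR or PR at least once. The word confirmed is absent from that definition.

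**The concern.** An analyst who follows Section 8 as written would report a rate and interval for a broader quantity than the listed endpoint. Section 7.1.1 asks sites to record events and symptoms linked to cancer progression or general deterioration. A patient with refractory metastatic disease can therefore have a Grade ≥3 event judged unrelated, which counts in the planned rate but not in endpoint 5. The trial has one arm, so no control group shows the background rate of such events.

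For duration of response, a patient with PR at one 12-weekly scan and progression at the next would be a non-responder for the response rate. The same patient would enter the duration analysis if its definition is taken literally. The two summaries would then describe different sets of patients under the same word, responders.

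In both cases the choice between two quantities could be left until the data have been seen.

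**Working it through.** The plan gives no figure for either quantity, so there is nothing to reproduce. The check compares the definitions and then works out what one patient is worth.

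**1. Definitions side by side**

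| Quantity | Section 2 or response-rate definition | Section 8 analysis |
|---|---|---|
| Grade ≥3 adverse events | Treatment-related only (Section 2, endpoint 5) | No relatedness qualifier; any cause under Section 7.1.1 |
| Responders | Confirmed PR or CR (response rate, Section 8) | CR or PR at least once (duration of response, Section 8) |

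Patients with a related Grade ≥3 event are a subset of patients with any Grade ≥3 event. With the same denominator, the any-cause rate is therefore greater than or equal to the related rate.

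**2. Size of the safety gap**

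Let k be the number of treated patients whose only Grade ≥3 events are unrelated. The gap is k/n. The denominators are n = 25 (initial enrollment, taking all 25 as treated, in line with the replacement rule in Section 4.5) and n = 41 (the proposed expansion). The documents give no value of k, so the range 0 to 4 is an assumption.

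- One patient: 1/25 = 4.0 points; 1/41 = 2.4 points.
- Four patients: 4/25 = 16.0 points; 4/41 = 9.8 points.
- Range: 0 to 16.0 points at n = 25; 0 to 9.8 points at n = 41.

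**3. Scale against precision**

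The plan names no interval method. For illustration, the exact binomial limits for x events in n patients are the 2.5% quantile of Beta(x, n − x + 1) and the 97.5% quantile of Beta(x + 1, n − x).

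| x/n | Rate | Exact 95% CI | Width (points) |
|---|---|---|---|
| 12/25 | 48.0% | 27.8 to 68.7% | 40.9 |
| 13/25 | 52.0% | 31.3 to 72.2% | 40.9 |
| 20/41 | 48.8% | 32.9 to 64.9% | 32.0 |
| 21/41 | 51.2% | 35.1 to 67.1% | 32.0 |

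An example with assumed counts: if 18 of 25 patients had any Grade ≥3 event and 15 of 25 had a related one, Section 8 as written would report 72% (50.6 to 87.9%). Endpoint 5 would be 60% (38.7 to 78.9%). The difference is 3/25 = 12 points.

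**4. Size of the duration-of-response mismatch**

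Let c be the number of confirmed responders and u the number of unconfirmed responders. The unconfirmed share of the duration set is u/(c + u). The smallest count that reaches the 45% response-rate trigger in 25 patients is 12 (12/25 = 48.0%; 11/25 = 44.0%). The values u = 1 to 3 and the alternative c = 6 are assumptions.

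| c | u = 1 | u = 2 | u = 3 |
|---|---|---|---|
| 12 | 1/13 = 7.7% | 2/14 = 14.3% | 3/15 = 20.0% |
| 6 | 1/7 = 14.3% | 2/8 = 25.0% | 3/9 = 33.3% |

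**The case against.** The strongest reply on safety is context. The Section 8 text runs through the secondary endpoints in roughly the order of Section 2, and the Grade ≥3 sentence stands where endpoint 5 would be analysed. It may simply be shorthand, with Section 2 supplying the restriction. That may well be the intent. But adverse event and related are separately defined terms in Section 7.1.1, and the sentence uses the unrestricted one.

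A second reply is that the general descriptive paragraph already covers endpoint 5 as a safety variable. A count and percentage might follow from it, but only where judged appropriate and without an interval.

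It is also fair that an any-cause rate properly serves the unqualified safety objective. The mismatch is with endpoint 5 alone.

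On duration of response, the confirmed definition appears shortly before in the same paragraph. Reaching a response at least once could mean that later loss of response does not remove a patient, rather than that confirmation is waived. The text does not say outright that unconfirmed responses count. This half rests on the parenthetical definition leaving out confirmation, and it is the weaker of the two.

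Finally, the sizes above come from assumed counts, and even the largest assumed safety gap (16 points) is smaller than the interval width of about 41 points at n = 25. That limits the importance of the point; it does not make the two quantities the same.

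**Conclusion.** The concern holds. Taken with the Section 7.1.1 definition, the Section 8 safety estimate is a broader quantity than secondary endpoint 5, and no passage commits to an estimate and interval for endpoint 5 itself. The definition of responders for duration of response, read literally, also differs from the one used for the response rate.

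The true safety gap cannot be derived from the documents and may be zero; it can only be in the upward direction. No direction is claimed for duration of response. The consequences are modest: the underlying data are collected either way, neither analysis feeds a decision rule, and the expansion trigger (median PFS or response rate) does not depend on them. The correction is worth making because a listed endpoint and its planned analysis should be the same quantity, and this should be settled before results are known.

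**What to change.** In Section 8:

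1. State that the point estimate and 95% confidence interval are for the proportion of treated participants with at least one Grade ≥3 adverse event classified as related under Section 7.1.1. Keep the rate of Grade ≥3 events of any cause as a supportive summary for the general safety objective.
2. Define the duration-of-response set as the participants with confirmed CR or PR who are counted in the response rate.

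The cost is a few words. The investigator already assesses relatedness, and confirmation must be determined for the response rate, so no new data are needed. The one drawback is that the duration-of-response set may be slightly smaller.

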4 STUDY ASSESSMENTS AND PROCEDURES

4.1 Pre-Treatment Period

During the Pre-Treatment Period, subjects are consented and qualified (screened) for the study. Informed consent must be obtained before initiation of any clinical screening procedure that is performed solely for the purpose of determining eligibility for this study. Evaluations performed as part of routine care before informed consent can be considered as screening evaluations if done within the defined screening period, and if permitted by the site's institutional review board (IRB)/ethics committee (EC) policies.

Study eligibility is based on meeting all of the study inclusion criteria and none of the exclusion criteria at screening and on Study Day 1 before study treatment administration. The following assessments will be conducted before subjects receive their first dose of treatment on this protocol:

Screening Procedures	Pre-treatment Period Day -28 through initiation of treatment	Instructions
Informed Consent	X	
Medical History	Х	All medical history relevant to the disease under study including smoking history, alcohol use, AJCC M stage, recreational drug use
Adverse Event Collection	Х	
Concomitant Medications	Х	Complete review of current medications with patient including herbal and dietary supplements, and over the counter (OTC)
Comprehensive Physical Exam	Х	To include basic body systems

Vital Signs	Х	Height, weight, blood pressure, pulse, 02 saturation, respiration
ECOG Performance Status	Х	
Disease Assessment	Х	Contrast enhanced CT of the chest, abdomen, pelvis Or MRI abdomen, w/wo gadolinium contrast including non contrast CT are acceptable for patients with iodine contrast allergies.
Cardiac Assessment	Х	ECHO and ECG
Biopsy	х	Optional biopsy prior to initiation of treatment. In patients who do not consent then archival tissue will be requested.
Laboratory Assessments	Х	See Clinical Safety Laboratory Assessments.
Tumor Markers	Х	LDH
Specimen Collection or Optional Specimen Banking	Х	Serum for banking (4ml lavender top and 4ml red top)

For each subject, the Pre-Treatment Period ends upon receipt of the first dose of study treatment or final determination that the subject is ineligible for the study.

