4.4 Correlative Studies

Translational studies will be performed on fresh tumor biopsies and peripheral blood specimens and correlated with clinical response to therapy.

- Paired tumor biopsies (pre-treatment and day #15) on 10 subjects with accessible tumors amenable to safe biopsy.
- PBMCs and serum will be collected pre-treatment and on day 1 of each cycle for the first 6 cycles.
- Analysis may include multiplex immunofluorescent tissue staining for characterization of tumor
 infiltrating immune profile, RNAseq to evaluate global gene expression changes within tumor
 resulting from treatment, and characterization of peripheral blood immune cell profiles, T cell
 activation status, and cytokine analysis. Scope of work and budgets will be negotiated with BMS
 and Exelixis separate from this clinical trial protocol.

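### Section 8 names only a paired t-test or Wilcoxon test for gene expression change, with no unit of testing, alpha or multiplicity control, although global RNAseq on at most 10 biopsy pairs is foreseen

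*Combined protocol and SAP*

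**What the plan says.** Section 2 lists "Correlative molecular profiling" as the sixth secondary endpoint and does not mark it as exploratory. Section 4.4 plans "Paired tumor biopsies (pre-treatment and day #15) on 10 subjects with accessible tumors amenable to safe biopsy". Among the analyses that may be done it names "RNAseq to evaluate global gene expression changes within tumor". Section 8 covers the analysis in one sentence: a "paired t-test or Wilcoxon signed-rank test will be performed to evaluate tumor infiltrating immune cell profiling and gene expression changes" from before to after treatment.

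The documents do not state the unit of testing, the number of genes or features, an alpha or sidedness for these tests, a rule for choosing between the two tests, or any multiplicity or false discovery rate (FDR) method. The only alpha in the plan, a "one-sided test given a type I error rate of 0.05", belongs to the PFS sample size.

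**The concern.** Both named tests handle one variable at a time, while the assay is described as global. The natural way to follow the sentence is to run the test once per gene, thousands of times, on 10 pairs. Without error control, noise alone produces a long list of changed genes. If a correction is added later, one of the two permitted tests has a smallest attainable p-value that limits what any correction can find.

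What is at stake is the mechanistic reading. Section 1.3 predicts the direction of change under VEGF inhibition for three populations: CD8+ T cells up, Treg and MDSC down. The paired biopsies are how the trial can look at this. As written, nothing separates those few hypothesis-driven contrasts from a transcriptome-wide screen, and the choice of test stays open until the data are seen.

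**Working it through.** The plan gives no calculation for this endpoint, so there is no stated figure to reproduce.

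**Inputs.** Pairs: n = 10 (Section 4.4). The screening table in Section 4.1 describes an "Optional biopsy prior to initiation of treatment", so fewer complete pairs are possible. Genes tested: m is not stated; I assume 20,000, range 10,000 to 25,000. Alpha: not stated; I assume 5% two-sided.

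**1. False calls without correction.** Expected number = alpha × m when every gene is null.
- m = 20,000: 0.05 × 20,000 = 1,000
- m = 10,000: 500; m = 25,000: 1,250

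The exact Wilcoxon test at n = 10 has actual size 0.0488, so its count is almost the same.

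**2. Smallest Wilcoxon p-value.** Exact two-sided floor = 2/2^n.
- n = 10: 2/1024 = 0.00195
- n = 8: 0.0078; n = 6: 0.031

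**3. Floor against Bonferroni.** Threshold = 0.05/m. At m = 20,000 this is 2.5 × 10⁻⁶, and the floor is 0.001953/0.0000025, about 781 times too high (391 to 977 times over the range). With 10 pairs, Bonferroni can be met for at most 25 tests (0.05/0.001953 = 25.6).

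**4. Floor against Benjamini-Hochberg (BH).** BH rejects the k smallest p-values if the k-th is at most q × k/m. No p-value is below the floor, so k ≥ floor × m/q.
- q = 5%, m = 20,000: 0.001953 × 20,000/0.05 = 781.25, so k ≥ 782 (391 at 10,000; 977 at 25,000)
- q = 10%, m = 20,000: k ≥ 391

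This is a minimum number of joint rejections. The genes need not all be at the floor, because BH is a step-up procedure. Example: 500 genes at 2/1024, 1,100 at the next attainable value 4/1024, the rest above 0.05. Then p(1600) = 0.0039 ≤ 0.05 × 1,600/20,000 = 0.0040, and all 1,600 are rejected.

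**5. What BH-corrected Wilcoxon can find.** Simulation with n = 10, 20,000 independent genes and normal changes (all assumptions):

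| Share changed | Change (SD) | FDR level | True changes found |
|---|---|---|---|
| 10% | 1.5 | 5% | about 1,000 of 2,000 |
| 5% | 2.0 | 5% | about 800 of 1,000 |
| 20% | 1.0 | 10% | about 1,900 of 4,000 |
| 5% or 10% | 1.0 | 5% | none |

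**6. The paired t-test.** It has no floor. At the Bonferroni level for 20,000 genes, its power with 10 pairs is 0.15% for a standardized change of 1.0 and 6.7% for 2.0.

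**7. Share of uncorrected calls that are false.** With pi the share of genes truly changed, share = 0.05(1 − pi)/[0.05(1 − pi) + pi × power]. Paired t power at 5% with 10 pairs is 29%, 62%, 80% and 99% for standardized changes of 0.5, 0.8, 1.0 and 1.5. At pi = 1% the false share runs from 94% down to 83% across those changes; at pi = 20%, from 41% down to 17%. False calls are the majority only if pi is below 14.6%, 7.5%, 5.9% or 4.8% respectively.

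**The case against.** The strongest reply is that the plan is silent, not wrong. It nowhere says that testing is gene by gene or that p-values stay unadjusted, and its sentence fits a few signature scores or selected transcripts equally well. That stands: both are inferences from silence, and the false-call figures hold only under that reading.

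Three stronger readings are tempting, and the documents support none of them.
- A reader might infer that most genes called changed would be false. That depends on the share of genes truly changed and the size of the changes, and the plan gives neither. Step 7 shows false shares from 17% to 94%.
- A reader might infer that the Wilcoxon floor rules out genome-wide testing. That is strict for Bonferroni only. Under BH the test works when many genes change strongly and fails when few do or changes are small (step 5).
- A reader might infer that the floor condemns the whole plan. It affects one of two permitted tests; the paired t-test has no floor.

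The reply also bears on weight. Section 4.4 is permissive ("Analysis may include multiplex immunofluorescent tissue staining for characterization of tumor", with RNAseq in the same list), and it leaves scope and budget to be negotiated outside the protocol, so a detailed pipeline could sit elsewhere. The trial calls itself a signal-seeking pilot, and its expansion rule uses only median PFS and ORR. This lowers the severity. It does not remove the point: the endpoint is listed as secondary, and the one analysis sentence names a method that does not suit a global screen on 10 pairs.

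**Conclusion.** The point holds as an under-specified analysis for which a better method is readily available. Under a gene-wise reading at two-sided 5%, about 5% of unchanged genes would be called changed, roughly 1,000 per 20,000 null genes. With 10 pairs the Wilcoxon option cannot go below p = 0.00195. That excludes it under genome-wide Bonferroni and costs it power under BH when few genes change, because at least 782 joint rejections are needed at 20,000 genes and 5% FDR. Fewer complete pairs make the floor worse.

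The gene count, the two-sided 5% level and gene-wise testing are my assumptions; the 10 pairs and the two tests are the plan's. Severity is low: neither the primary endpoint nor any trial decision depends on it. I would class it as a cheap improvement.

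**What to change.** In Section 8, split the endpoint in two.

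- **Hypothesis-driven part.** Name a few contrasts from Section 1.3 (CD8+, Treg, MDSC). State one paired test or the rule for choosing it, the alpha and sidedness, and how multiplicity is handled. The Wilcoxon test is workable here: for three contrasts the Bonferroni threshold is 0.05/3 = 0.0167, above the floor with 10 pairs (0.00195) or 8 pairs (0.0078), though not with 6 (0.031).
- **Genome-wide part, if RNAseq is done.** Use a moderated (variance-shrinkage) or count-based paired model with Benjamini-Hochberg control at a stated FDR level, in place of gene-wise Wilcoxon tests. Label this screen exploratory.

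The cost is a few lines of SAP text and standard software, and fewer genes will be called changed. Patients, visits and samples are unaffected.
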